5.6. Safety Endpoints and Analysis

5.6.1. Descriptive Analyses

All adverse events, measures of pain and discomfort, changes in ocular surface staining, changes in IOP, and chances in BCVA (EDTRS) will be tabulated by visit and treatment group.

5.6.2. Safety Endpoints

- The difference in the incidence of non-ocular adverse events, between subjects in the study arm and subjects in the control arm
- The difference in the incidence of ocular adverse events, between subjects in the study arm and subjects in the control arm
- The difference in the incidence of unanticipated serious adverse events, between subjects in the study arm and subjects in the control arm
- The difference in the level of pain/discomfort during IPL treatment, between subjects in the study arm and subjects in the control arm
- The difference in the level of pain/discomfort during MGX, between subjects in the study arm and subjects in the control arm
- The difference in the change of biomicroscopy immediately before and immediately after IPL treatment, between subjects in the study arm and subjects in the control arm

5.6.3. Primary Safety Analysis

The safety endpoints will be summarized for each treatment group.

We will compute the incidence of ocular adverse events as a simple proportion, counting the number of subjects with any event (that is, counting the first event per person).

5.7. Effectiveness analyses

The primary efficacy outcome measure (TBUT) consist of a pre-treatment measurement (the baseline), a treatment intervention, and a post-treatment measurement (the follow-up). Both eyes will be included in the analysis. Since the two eyes of a subject are not independent, to estimate whether TBUT has improved from the baseline to the follow-up, a linear mixed effects model with random intercept, using the subject identity as the random effect, is the appropriate test. Since there are two eyes per person then there is only one possible covariance structure (i.e. symmetric, with a single correlation between eyes).

The secondary efficacy outcome measures are OSDI and EDS which will be collected at the baseline, and at a follow-up visit. In the case of OSDI, the value is estimated per subject. Hence, a single value will be collected per subject at each of these two visits. In this case a paired t-test is the appropriate statistical test to estimate whether dry eye symptoms have improved, using the change of OSDI from baseline to the follow-up. In the case of EDS, the value is estimated per eye. Hence, two values will be collected per subject at each of these two visits. Since the two eyes of a subject are not independent, to estimate whether EDS has improved from the baseline to the follow-up, a linear mixed effects model with random intercept, using the subject identity as the random effect, is the appropriate test. The level of

statistical significance is $\alpha = 0.05$. Non-parametric tests will be performed if the underlying distributions are not normal.

For all other eye-level analyses, where appropriate, sample means of continuous variables will be analyzed with linear mixed effects model with random intercept (whenever both eyes of a subject are included in the analysis), or two-sample t-tests. Proportions will be analyzed with χ^2 tests.

All statistical tests will be two-sided because potentially the treatment procedure may worsen the outcome. The level of statistical significance (type I error) is $\alpha = 0.05$. Non-parametric tests will be performed if the underlying distribution is not normal.

For descriptive statistics, the N, Mean, Median, Standard deviation, Standard error of the mean, 95% confidence interval, Minimum, and Maximum will be reported for continuous variables; the frequency and proportion for each category will be reported for nominal and categorical variables.

A previous study demonstrated that in subjects with a lower TBUT at the baseline, the change in TBUT at the follow-up was larger [21]. Although not shown in this study, the severity level of skin rosacea at the baseline may also be a confounder. Hence, in addition to the primary analysis, we will carry out an analysis of covariance (ANCOVA) to adjust for these covariates.

The following baseline covariates will be included in the ANCOVA:

- (1) TBUT at baseline. This covariate will be treated as continuous.
- (2) The 4-point severity level of skin rosacea at baseline (0= none; 1 = mild; 2 = moderate; 3 = severe). This covariate will be treated as either a numeric score (continuous) or using orthogonal polynomial contrasts.

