1.2. Rationale of the Study

A number of recent prospective studies demonstrated that IPL treatment as monotherapy or in combination with MGX gave some relief to signs and symptoms of DED due to MGD. In all of these studies, the main limitation was that the study was designed as a single arm trial. Hence, at least part of the relief observed in these studies could result from a placebo effect.

The aim of the current prospective study is to examine the contribution of the IPL treatment *itself*. For the first time, the effect of IPL will be examined in a study designed as a blinded randomized controlled trial. Subjects in the study arm will be treated with IPL followed by MGX, while subjects in the control arm will be treated with sham IPL followed by MGX. A significant difference in the outcomes of the two arms will provide support for a genuine contribution of the IPL treatment. In addition, it is expected that subjects in the study arm might feel less pain during MGX, as the heat transferred from the site of IPL administration to the meibomian glands may liquefy the meibum thus facilitating expression.

2. The Investigational Device

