8.3.2. Anticipated Benefits

For patients in the study arm, the anticipated benefit that may be observed in this study is the relief of signs and symptoms of DED, as measured by the tests and surveys required in this protocol. In addition, a previously proven benefit from IPL treatments, while not the objective of this study, is improvement in the appearance of the skin in the treated area.

Patients in the control arm may experience a smaller improvement of their signs and symptoms of DED, possibly due to a placebo effect.

9. Administrative Procedures

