9.7. Modification of Protocol

The protocol may be amended with the written agreement of the Sponsor and upon notification of and approval by the IRB. Investigators should review the contents of the amended protocol. Subsequent alterations should only be made in written conjunction with the Sponsor.

Medically significant amendments to the protocol (e.g., changes that increase the risk or the inconveniences for the patient, changes to the inclusion/exclusion criteria, etc.) must be approved by the IRB prior to implementation.

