 Ocular surface abnormality that may compromise corneal integrity in either eye (e.g., prior chemical burn, recurrent corneal erosion, corneal epithelial defect, Grade 3 corneal fluorescein staining, or map dot fingerprint dystrophy)
• Eyelid abnormalities that affect lid function in either eye, including: entropion, ectropion, tumor, edema, blepharospasm, lagophthalmos, severe trichiasis, and severe ptosis
 Any systemic condition that may cause dry eye disease, including: Stevens-Johnson syndrome, vitamin A deficiency, rheumatoid arthritis, Wegener's granulomatosis, sarcoidosis, leukemia, Riley-Day syndrome, systemic lupus erythematosus, and Sjögren's syndrome

	• Unwilling or unable to abstain from the use of medications known to cause dryness (e.g., isotretinoin, antihistamines) throughout the study duration. Subjects must discontinue these medications for at least 1 month prior to the baseline visit.			
	Any condition revealed whereby the investigator deems the subject inappropriate for this study			
	Primary objectives TBUT estimated at the single FU (Between 4 weeks -3 days and 4 weeks + 7 days after the final treatment)			
Objectives	Measurement of TBUT will be implemented using FUL-GLO® fluorescein ophthalmic strips. Three successive readings will be taken and averaged to a single value.			
	Secondary objectives Self-evaluation of OSDI at the single FU, using the OSDI questionnaire Self-evaluation of Eye Dryness Score (EDS) at the single FU, using a VAS			
	Primary endpoint:			
	The difference in the change of TBUT from BL to FU, between eyes in the study arm and eyes in the control arm			
	The improvement of TBUT in eyes of the study arm is larger than the improvement of TBUT in eyes of the control arm, where improvement is defined as a positive change of TBUT from BL to FU			
	Secondary endpoints			
Criteria for Evaluation	The difference in the change of OSDI from BL to FU, between subjects in the study arm and subjects in the control arm			
	The difference in the change of EDS from BL to FU, between subjects in the study arm and subjects in the control arm			
	The improvement of OSDI in the study arm is larger than the improvement of OSDI in the control arm, where improvement is defined as a negative change of OSDI from BL to FU			
	arm, where improvement is defined as a negative change of OSDI from BL to FU			

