5.2. Secondary Study Hypotheses

 The change of OSDI (△OSDI) in subjects of the study arm is *more negative* than △OSDI in subjects of the control arm, where △OSDI is defined as OSDI at the follow-up minus OSDI at the baseline:

H0: $\triangle OSDI_S \ge \triangle OSDI_C$

H1: $\triangle OSDI_S < \triangle OSDI_C$

 The change of EDS (△EDS) in subjects of the study arm is *more negative* than △EDS in subjects of the control arm, where △EDS is defined as EDS at the follow-up minus EDS at the baseline:

> H0: $\triangle EDS_{S} \ge \triangle EDS_{C}$ H1: $\triangle EDS_{S} < \triangle EDS_{C}$

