5.7.2. Analysis Model

The linear mixed effects model for TBUT can be written as follows:

$$y_{ij} = \beta_0 + \beta_1 T_i + \beta_2 TBUT_{ij,0} + b_{0i} + \epsilon_{ij}$$

Where

- $TBUT_{ij,k}$ is the TBUT value for subject i, eye j, week k.
- y_{ij} is the 1 month change from baseline TBUT for subject i, eye j. $y_{ij} = TBUT_{ij,4} - TBUT_{ij,0}$
- T_i is the binary treatment indicator for subject i (0 = Control, 1 = IPL Laser)
- $\beta_0, \beta_1, and \beta_2$ are the fixed effect parameters:
 - \circ β_0 is the mean change from baseline for the Control arm,
 - β_1 is the difference between IPL and Control in mean change from baseline,
 - \circ β_2 is the effect of each unit change in baseline TBUT.

- b_{0i} is the random effect (random intercept term) for subject i $b_{0i} \sim N(0, \sigma_a^2)$
- ϵ_{ii} is the normally-distributed error term ٠ $\epsilon_{ij} \sim N(0, \sigma_e^2)$
- $\{b_{0i}\}$ and $\{\epsilon_{ii}\}$ are independent

The linear mixed effects models can be fit in SAS or R as follows:

In SAS:

Proc Mixed data=IPLdat method=ml; class SUBJ TRT; model TBUT_DIFF = TRT TBUT_BL / solution; random intercept / subject=SUBJ;

In R:

Library(Ime4) fit.tbut <- Imer(TBUT.DIFF ~ TRT + TBUT.BL + (1|SUBJ), REML=FALSE, data=IPLdat)

Note that since we are interested in testing the fixed effects, ML (maximum likelihood) versus REML (residual maximum likelihood) estimates are being used.

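### The OSDI hypothesis compares the two arms, but the plan tests it with a paired t-test, which cannot compare them

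*SAP*

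**What the plan says.** The endpoint is between-arm. The SAP synopsis, under Criteria for Evaluation, gives it as "The difference in the change of OSDI from BL to FU, between subjects in the study arm and subjects in the control arm". SAP 2.3 and 4.1.2 and Protocol 3.5.3 and 6.1.2 define it the same way. SAP 5.2 and Protocol 7.2 state the matching hypothesis: the alternative is that the change in OSDI is more negative in the study arm than in the control arm.

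The test is not between-arm. SAP 5.7 and Protocol 7.4 note that OSDI yields one value per subject per visit and continue: "In this case a paired t-test is the appropriate statistical test to estimate whether dry eye symptoms have improved". The variable named is the change from baseline to follow-up. No arm is mentioned. The fallback is equally unspecific: "Non-parametric tests will be performed if the underlying distributions are not normal".

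Protocol 1.2 says what the trial's inference should rest on: "A significant difference in the outcomes of the two arms will provide support for a genuine contribution of the IPL treatment".

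**The concern.** A paired t-test on OSDI change tests whether the mean change is zero. The stated hypothesis is that the mean change differs between arms. The first can be rejected when the second null hypothesis is true.

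That situation is plausible in this trial. Both arms receive meibomian gland expression after active or sham IPL. Entry requires OSDI of at least 23, so some fall at follow-up is expected from regression to the mean. Protocol 8.3.2 itself allows for a control response: "Patients in the control arm may experience a smaller improvement of their signs and symptoms of DED, possibly due to a placebo effect". A paired test would combine all of this with any IPL effect. Protocol 1.2 criticises earlier single-arm studies for the same weakness.

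An analyst who follows SAP 5.7 literally runs a test that does not address the OSDI hypothesis. One who departs from it uses a test that was not prespecified. OSDI is one of only two secondary efficacy endpoints, and the study title refers to symptoms as well as signs.

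**Working it through.** **1. Does another section supply the missing test?**

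| Place | What it covers | Tests OSDI change between arms? |
|---|---|---|
| SAP 5.7, two-sample t-tests | The remaining eye-level analyses | No. OSDI is per subject and already has its own test |
| SAP 5.7, χ² tests | Proportions | No. At most the exploratory OSDI < 23 proportion |
| SAP 5.7, ANCOVA | Addition to the primary analysis, adjusting for baseline TBUT and rosacea | No |
| SAP 4.1.1 | TBUT mixed model and success criterion | No |
| SAP 5.7.1 | Stratified ANOVA of TBUT change | No |
| SAP 5.7.2 | "The linear mixed effects model for TBUT can be written as follows" | No. The treatment term is in the TBUT model only |

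SAP 5.7 also describes the TBUT analysis as estimating improvement from baseline. For TBUT, however, SAP 4.1.1 and 5.7.2 state the arm comparison. OSDI has no equivalent passage.

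**2. The plan's own sizing figure.** The only sizing is for TBUT: means 5 and 1 sec, SD 5, two-sided alpha 0.05, power 80%. The normal approximation gives n per arm = 2 × (1.960 + 0.842)² × 5² / 4² = 24.5, so 25 per arm and 50 in total, as stated. There is no corresponding figure for OSDI.

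**3. Inputs for the OSDI calculation.**
- From the documents: 83 evaluable subjects randomised 1:1, taken as 42 IPL and 41 sham; two-sided alpha 0.05.
- Assumed, because the documents give no values: the same true improvement m in both arms (0, 3, 5 or 10 points), SD of change s of 15 or 20, and normally distributed changes.
- The true difference between arms is zero throughout, so every rejection read as an IPL benefit is false.

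**4. Formula.** With d = m/s, the paired t statistic follows a noncentral t distribution with n − 1 degrees of freedom and noncentrality d√n. The rejection probability is P(|t| > t₀.₉₇₅,ₙ₋₁). Example: m = 3 and s = 15 give d = 0.2. With n = 42 the noncentrality is 0.2 × √42 = 1.296, the critical value is 2.02, and the rejection probability is 0.244.

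The plan does not say whether the paired test is run in the IPL arm, in each arm or on all subjects, so three readings are shown. For the second, the arms are independent and the probability is P₄₂ × (1 − P₄₁).

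| Shared improvement, SD | d | IPL arm significant (n = 42) | IPL significant, sham not | All 83 pooled |
|---|---|---|---|---|
| 0 | 0 | 0.050 | 0.048 | 0.050 |
| 3, SD 20 | 0.15 | 0.158 | 0.133 | 0.272 |
| 3, SD 15 | 0.20 | 0.244 | 0.186 | 0.437 |
| 5, SD 20 | 0.25 | 0.353 | 0.231 | 0.614 |
| 5, SD 15 | 0.33 | 0.559 | 0.252 | 0.851 |
| 10, SD 20 | 0.50 | 0.886 | 0.108 | 0.994 |
| 10, SD 15 | 0.67 | 0.988 | 0.014 | >0.999 |

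**5. Comparison.** A two-sample t-test of the changes, simulated 100,000 times per scenario, rejects in 4.9–5.1% whatever the shared improvement.

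**6. Fallback.** The plan names no non-parametric test. The natural counterpart of a paired t-test is the Wilcoxon signed-rank test, also within-subject. With n = 42 and 20,000 simulations it rejects in 0.048 (no improvement), 0.151 (3, SD 20), 0.337 (5, SD 20), 0.537 (5, SD 15) and 0.872 (10, SD 20). It has the same defect.

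**The case against.** **The between-arm quantity is prespecified, and this may be a drafting slip.** SAP 4.1.2 says the arm difference in OSDI change will be estimated, SAP 5.2 gives between-arm hypotheses, and no passage says a significant paired test would establish them. The improvement-from-baseline wording is also used for TBUT, which is certainly compared between arms. A slip is plausible, but the same section uses the term two-sample t-test elsewhere, so the plan distinguishes the two procedures. The stated intention also does not replace the test that is named.

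**Study success does not depend on OSDI.** That is correct. The success criterion uses TBUT alone, which limits the consequence to one secondary hypothesis.

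**The figures are hypothetical.** They are. The range from 5% to 99% reflects the absence of OSDI assumptions in the documents. The one control-arm improvement the plan quantifies, TBUT 1 ± 5 sec (0.2 SD), need not carry over to a symptom score. If it did, the IPL-arm rate would be 24%.

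**The analysed number may be smaller.** SAP 3.3 places secondary analyses on the per-protocol set. If the 8 incorrectly treated IPL subjects were excluded, which the plan does not state, n would be 42 − 8 = 34. The rate would then fall from 24.4% to 20.5% at 0.2 SD and from 89% to 81% at 0.5 SD. The conclusion is unchanged.

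**EDS has similar wording.** SAP 5.7 describes the EDS model without an arm term too. A mixed model can carry one and a paired t-test cannot, so EDS is a separate and lesser matter.

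**Conclusion.** The concern holds. SAP 5.7 and Protocol 7.4 assign OSDI a test that cannot evaluate the hypothesis in SAP 5.2 and Protocol 7.2, and no other section repairs this. This does not depend on any numerical assumption.

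The size does. With equal true improvement in both arms, normally distributed changes and 42 IPL subjects, the false-positive rate is 5% only when there is no improvement at all. It exceeds half at 5 points with SD 15, and reaches 89–99% at 10 points. Reading significance in the IPL arm but not in the sham arm as evidence of benefit does not restore control: across the scenarios with improvement it occurs in 1–25%.

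The sentence must be corrected, because following it as written gives the OSDI hypothesis no valid test. The primary TBUT conclusion is not affected.

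**What to change.** Replace the paired t-test sentence in SAP 5.7 and Protocol 7.4 with text such as:

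> Change in OSDI from baseline to follow-up will be compared between arms with a two-sample t-test. The between-arm difference, its 95% CI and the two-sided p-value test the OSDI hypothesis (SAP 5.2, Protocol 7.2). If the distribution is not normal, a Wilcoxon rank-sum test between arms will be used. Within-arm paired changes are descriptive only.

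This is the minimum. An ANCOVA with treatment and baseline OSDI would be preferable but is optional. If a site term is added, it should use the A1, A2, B and C strata of SAP 5.7.1.

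The cost is a SAP revision and a wording amendment to the protocol. On the latter, Protocol 9.7 says: "The protocol may be amended with the written agreement of the Sponsor and upon notification of and approval by the IRB". No new data are needed, since OSDI is already collected at baseline and follow-up.

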	 In either eye, severe (Grade 4 on the EFRON scale) inflammation of the eyelid, including: blepharochalasis, staphylococcal blepharitis or seborrheic blepharitis
	 Ocular surface abnormality that may compromise corneal integrity in either eye (e.g., prior chemical burn, recurrent corneal erosion, corneal epithelial defect, Grade 3 corneal fluorescein staining, or map dot fingerprint dystrophy)
	 Eyelid abnormalities that affect lid function in either eye, including: entropion, ectropion, tumor, edema, blepharospasm, lagophthalmos, severe trichiasis, and severe ptosis
	 Any systemic condition that may cause dry eye disease, including: Stevens-Johnson syndrome, vitamin A deficiency, rheumatoid arthritis, Wegener's granulomatosis, sarcoidosis, leukemia, Riley-Day syndrome, systemic lupus erythematosus, and Sjögren's syndrome
	• Unwilling or unable to abstain from the use of medications known to cause dryness (e.g., isotretinoin, antihistamines) throughout the study duration. Subjects must discontinue these medications for at least 1 month prior to the baseline visit.
	Any condition revealed whereby the investigator deems the subject inappropriate for this study
	Primary objectives TBUT estimated at the single FU (Between 4 weeks -3 days and 4 weeks + 7 days after the final treatment)
Objectives	Measurement of TBUT will be implemented using FUL-GLO® fluorescein ophthalmic strips. Three successive readings will be taken and averaged to a single value.
	Secondary objectives Self-evaluation of OSDI at the single FU, using the OSDI questionnaire Self-evaluation of Eye Dryness Score (EDS) at the single FU, using a VAS
	Primary endpoint:
	The difference in the change of TBUT from BL to FU, between eyes in the study arm and eyes in the control arm
Criteria for Evaluation	The improvement of TBUT in eyes of the study arm is larger than the improvement of TBUT in eyes of the control arm, where improvement is defined as a positive change of TBUT from BL to FU
	Secondary endpoints
	The difference in the change of OSDI from BL to FU, between subjects in the study arm and subjects in the control arm
QF-1044440 Rev. D	Global Clinical Study Report Template GEN-0010523 Effective Date: July-2017

	The difference in the change of EDS from BL to FU, between subjects in the study arm and subjects in the control arm			

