3.3.3. Follow Up visit

There will be a single follow-up visit at 4 weeks after the final treatment session. The subject can advance the follow-up visit session by up to 3 days, or delay the follow-up visit by up to 7 days. At the beginning of the follow-up visit, the subject will self-evaluate his/her symptoms using two tools: (1) the OSDI questionnaire; (2) the EDS score using a VAS.

The following assessments will be performed in both eyes by a masked examiner:

:

• Three consecutive readings of TBUT (before any other test)

Revision: C State: Released ECO No: ca-00000172 Effective Date: 19-Sep-2019

- Routine ophthalmology tests, including:
 - Biomicroscopy with the slit lamp
 - BCVA with an ETDRS chart
 - IOP measurement
- •
- Meibography
- Meibomian gland secretion score (MGS), using the method described by Lane and colleagues. [29]
- Capture of high-resolution photos of the upper and lower eyelids, including lid margins, irises and eyelashes

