5.1.5. Self-Assessment of Symptoms

To reduce the risk of bias, symptoms will be self-evaluated by the subject *before* any of the other specific tests (TBUT, MGS, and close-up photos of the eyelids) are performed by the study investigator(s).

Self-assessment of symptoms will be performed using 2 different methods:

- (1) Ocular Surface Disease Index (OSDI), using a questionnaire (developed by Allergan, Inc.) questionnaire. This questionnaire, which reports a single score for both eyes, is well-established for diagnosing symptoms of DED [30].
 - The questionnaire will be filled-out by the subject
 - The subject will grade 12 questions related to: ocular symptoms (3 questions), vision-related function items (6 questions) and environmental triggers items (3 questions)
 - Each of the 12 items will be scored from 0 to 4, where 0 indicates "never" and 4 indicates "always"
 - The questionnaire should take 5 minutes to complete.
 - OSDI will be calculated as the sum of the answered scores times 25, divided by the number of questions answered (range: 0 to 100).
 - Based on the OSDI, a subject can be categorized as having a normal ocular surface (0-12 points), mild symptoms (13-22 points), moderate symptoms (23-32 points), or severe symptoms (33-100 points), as described in [30].
 - OSDI at baseline is used for an inclusion criterion: to be included in the study, the subject must have OSDI ≥ 23 at baseline (moderate or severe symptoms).

QF-1044440 Rev. D	Global Clinical Study Report Template	GEN-0010523	Effective Date: July-2017

- (2) Eye Dryness Score (EDS), using a VAS. This questionnaire, which reports a single score for both eyes, has been used in other dry eye studies and was recently used as the primary symptom endpoint for FDA approval of lifitegrast for the treatment of signs and symptoms of dry eye (Xiidra, manufactured by Shire US, Inc.). EDS was accepted as a clinical outcome assessment by the division of transplant and ophthalmology at fda.gov (NDA 208073, June 2015)
 - The subject will be shown a 10 cm line, and will be asked to mark an X sign along the line
 - The subject will be instructed to mark the X sign on the leftmost side of the line if he/she does not have any symptoms of DED, on the rightmost side of the line if he/she has intolerable symptoms of DED, or somewhere along the line at a location that best represents his/her perception of symptoms in all other cases.

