	6. Self-assessment of pain/discomfort during IPL administration, using a VAS			
	7. Self-assessment of pain/discomfort during MGX, using a VAS			
	There will be a single follow-up (FU) visit, which will occur 4 weeks (-3 days, + 7 days) after the final treatment session. Subjects will undergo the following assessments, in the specified order:			
	 Subject's report of the daily usage (frequency and dose) of eye drop, warm compresses and lid hygiene since the previous visit 			
	2. Three consecutive measurements of TBUT in both eyes			
Follow-up (FU)	3. Routine ophthalmology tests in both eyes, including: biomicroscopy, BCVA and IOP			
visit	4. OSDI, self-assessed using an OSDI questionnaire			
	5. EDS, self-assessed using a VAS			
	6. High resolution close-up photos of both eyes, including: iris, lid margins and eyelashes			
	7. Meibography of the upper and lower eyelids in both eyes			
	8. Meibomian gland secretion (MGS) score in 15 glands of the lower eyelid in both eyes			
Safety outcome measures	 incidence of non-ocular adverse events throughout the study incidence of ocular adverse events throughout the study incidence of unanticipated serious adverse events throughout the study self-assessment of pain/discomfort of IPL in treatment sessions (using a VAS) self-assessment of pain/discomfort of MGX in treatment sessions (using a VAS) 			
Covariates	Baseline TBUT (continuous)Baseline skin rosacea (4-point scale)			
	The following assumptions were used to calculate the original sample size:			
Sample Size	(1) In the study arm, the change of TBUT from BL to FU \approx 5 \pm 5 sec (2) In the control arm, the change of TBUT from BL to FU \approx 1 \pm 5 sec			

	(3) A type I error of 0.05 (two-tailed test)				
	(4) A type II error of 0.2 (power = 0.8)				
	(5) A 1:1 ratio of Treatment to Control				
	With these assumptions, the minimal sample size was calculated to be 50 evaluable subjects (100 evaluable eyes): 25 subjects (50 eyes) in the control arm and 25 subjects (50 eyes) in the study arm.				
	Assuming a dropout rate of 15%, the anticipated number of enrolled subjects was 59. Assuming a screening failure rate of 15%, the anticipated total number of screened subjects was 69.				

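### EDS is described as one score per subject in Protocol 5.1.5 but as two per-eye values in Protocol 7.4 and SAP 5.7, which choose its model on that basis; the two must be reconciled

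*SAP*

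**What the plan says.** **How EDS is collected.** Protocol 5.1.5 introduces the scale with "This questionnaire, which reports a single score for both eyes, has been used in other dry eye studies". The procedure is "The subject will be shown a 10 cm line, and will be asked to mark an X sign along the line"; the measured distance is then scaled to 0–100. No step is repeated for the second eye. At follow-up, Protocol 3.3.3 says "the subject will self-evaluate his/her symptoms using two tools: (1) the OSDI questionnaire; (2) the EDS score using a VAS". The SAP synopsis lists "EDS, self-assessed using a VAS" for the same visit. The visit lists in both synopses specify both eyes for TBUT, the ophthalmology tests, photographs, meibography and MGS, but not for OSDI or EDS.

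**How EDS is analysed.** SAP 5.7, with the same text in Protocol 7.4, says "In the case of EDS, the value is estimated per eye. Hence, two values will be collected per subject". It reasons that the eyes are not independent and concludes: "to estimate whether EDS has improved from the baseline to the follow-up, a linear mixed effects model with random intercept". The endpoint in the Protocol synopsis is "The difference in the change of EDS from BL to FU, between subjects in the study arm and subjects in the control arm", and SAP 2.3 and 4.1.2 define it as change from baseline. SAP 5.7.2 opens with "The linear mixed effects model for TBUT can be written as follows" and gives an equation with a treatment term; no equation is given for EDS.

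**TBUT above 10 seconds (exploratory).** Both synopses, Protocol 3.5.4 and SAP 2.4 count eyes. Protocol 6.1.3 and SAP 4.1.3 refer to proportions of subjects but compare them between eyes. SAP 5.7 assigns a chi-square test to proportions and mentions no adjustment for pairing.

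**The concern.** The EDS model was selected because two values per subject were expected. If the form yields one value, that reason is gone. Fitted to one change score per subject, a random intercept and a residual error describe the same variation, and the data cannot tell them apart. EDS is one of only two secondary endpoints, so the analyst would have to choose its test at analysis rather than follow the plan.

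The exploratory proportion has a related weakness. SAP 5.7 recognises that fellow eyes are correlated and handles this for continuous eye-level variables, but not for proportions. If eyes are the unit, the p-value may be too small.

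**Working it through.** **1. Plan figures.** No power or sample size is stated for EDS or for TBUT above 10 seconds. The stated sample size concerns TBUT change. With a difference of 5 − 1 = 4, SD 5, two-sided 0.05 and 80% power, n per arm = 2 × (1.96 + 0.8416)² × 25/16 = 24.5, so 25 per arm and 50 in total, as stated. The adjusted 68 subjects also reproduce: with eye correlation 0.5, the SD of a subject's two-eye mean is 5 × √(1.5/2) = 4.33; with 8 IPL subjects set to the control mean, simulated power at 34 per arm is 0.80. Neither calculation uses EDS.

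**2. EDS, one change per subject.** With one row per subject, Var(yᵢ) = σₐ² + σₑ², so the likelihood depends only on the sum. Numerical checks on simulated data with 83 rows and a treatment term:

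- In one data set the log-likelihood is −392.308 at subject-variance shares of 0, 10, 25, 50, 75, 90 and 99%. In another it is −365.808 at 0, 25, 50, 75 and 100%.
- R's lmer, which SAP 5.7.2 names for TBUT, stops with an error because there are as many subjects as observations (fitted here without a baseline covariate).
- A Python mixed-model routine, not named in the SAP, does return a fit. It splits the variance equally (197.08 and 197.08) and warns about the Hessian. Its treatment standard error is 3.10, against 4.41 from ordinary regression on the same data (ratio 3.10/4.41 = 0.70).
- A two-sample t-test on one change per subject has simulated type I error of 0.050.

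**3. EDS, one score at each visit.** If baseline and follow-up scores enter as two rows per subject with a visit-by-treatment term, the random intercept is identifiable. In five simulated data sets of 83 subjects, the contrast and test statistic matched the two-sample t-test on change (for example −10.1801 and −2.9031 from both).

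**4. TBUT above 10 seconds, if eyes are the unit.** With two eyes per subject and binary correlation ρ, the variance of each arm's proportion is multiplied by 1 + ρ. The type I error of the uncorrected chi-square is therefore 2 × (1 − Φ(1.96/√(1+ρ))). The documents give no responder rate, no binary correlation and no form of the chi-square, so all three are assumptions. Simulations use 42 and 41 subjects, 40,000 null trials per cell and responder rates of 5, 10, 20, 30 and 40%.

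| Assumed correlation | Uncorrected, formula | Uncorrected, simulated | Continuity-corrected, simulated |
|---|---|---|---|
| Latent 0.5 (binary 0.20–0.33) | – | 7.7–8.9% | 2.8–6.6% |
| Binary 0.3 | 8.6% | 8.3–9.1% | 3.5–6.3% |
| Binary 0.5 | 11.0% | 10.9–11.6% | 4.9–8.5% |
| Binary 0.7 | 13.3% | 13.0–14.5% | 6.8–10.7% |

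The latent 0.5 is borrowed from SAP 5.3.2, where it applies to the TBUT change calculation. At that value, a t-test on each subject's share of responding eyes gives 4.7–5.0%. Counting subjects with at least one responding eye, the uncorrected chi-square gives 4.4–5.2%.

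**The case against.** It can be said in the plan's favour that the EDS model is never written as an equation. SAP 5.7 speaks of values at each of two visits and of improvement between them, so a visit-level model may be intended; with one score per visit that model works and agrees with the t-test on change. This stands as a limit: the identifiability failure is conditional. The change-score reading remains the likelier one, because SAP 2.3 and 4.1.2 define the endpoint as change and SAP 5.7.2 models change for TBUT.

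Four stronger readings are tempting and are not supported:

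- *The between-arm EDS model is missing even if two values exist.* SAP 5.7 describes TBUT and EDS in the same terms, SAP 5.7.2 shows that for TBUT this includes a treatment term, and SAP 5.2 fixes the EDS contrast as study against control. Extending the TBUT model is direct; writing it out only adds detail.
- *The endpoint wording proves a single score.* Comparing subjects between arms is compatible with two eyes per subject, since subjects are randomised. The conflict lies between Protocol 5.1.5 and the two analysis sections.
- *The form is known to record one score.* The form is not in the documents, and Protocol 5.1.5 uses the same single-score phrase for OSDI and EDS, so copied wording cannot be excluded. The one-line, one-mark procedure and the visit lists still favour a single score.
- *The EDS test has an inflated error rate.* Copying one score to both eyes and treating the copies as independent would give a type I error of about 0.166, but nothing in the plan proposes that.

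**Conclusion.** The conflict over the EDS unit is real and sits in a stated analysis rule for one of two secondary endpoints. If one score is recorded and the model is fitted to change from baseline, the variance components cannot be separated and the software output may fail or mislead. The treatment difference and total variance remain estimable, so a simple comparison of changes recovers a valid test. This should be corrected before the analysis is run.

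The proportion with TBUT above 10 seconds is a minor matter: one exploratory p-value, with an inconsistent unit. Any excess error depends on eyes being the unit, on correlations the documents do not give, and on the form of the chi-square; continuity correction lowers it, at low responder rates to below 5%. If subjects are the unit, chi-square is suitable.

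The primary TBUT model, the success criterion and the sample size do not depend on either issue.

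**What to change.** **EDS.** Confirm from the form in use whether one or two values are recorded per visit, then bring Protocol 5.1.5, Protocol 7.4 and SAP 5.7 into line.

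- If one: replace the per-eye mixed model with a between-arm comparison of one EDS change per subject, by two-sample t-test or by ANCOVA on baseline EDS. Name one of these in advance.
- If two: correct Protocol 5.1.5 and state that the SAP 5.7.2 model, with its treatment term, applies to EDS. The endpoint wording can stay.

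**TBUT above 10 seconds.** State whether eyes or subjects are counted and align both synopses, Protocol 3.5.4 and 6.1.3, and SAP 2.4 and 4.1.3. If eyes, use a subject-clustered method: compare each subject's share of responding eyes, or use logistic GEE with robust standard errors and a small-sample correction. Keep chi-square for subject-level proportions such as OSDI below 23.

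**Cost.** Wording only, with no new data or visits. If eyes are the unit, the exploratory p-value will usually be somewhat larger than from an uncorrected chi-square.
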